### Sensitivity Analyses

Because complete case approach assumes data are missing completely at random, we will use multiple imputation that assumes missing at random as a sensitivity analysis. We will create 100 imputed data sets using appropriate FCS model and combine results using Rubin's rules. We will also present estimates assuming "best case" (i.e., probability of event = 0) and "worst case" (i.e., probability of event = 1) scenarios. Of note, only participants who are deemed evaluable will be included in this primary analysis; therefore, very little (if any) missing data is expected. Sensitivity analyses related to missing data in the All Treated analysis set will be addressed in the supplementary analyses.

### Supplementary Analyses

Supplementary analyses for the secondary safety outcome measures will include all participants (Cohort 1-naïve and Cohort 1 rollovers) who received study products. All intercurrent events will be addressed using a while on treatment strategy, and missing data will be handled using a complete case approach. Because this approach assumes data are missing completely at random, we will use multiple imputation that assumes missing at random as a sensitivity analysis. We will create 100 imputed data sets using appropriate FCS model and combine results using Rubin's rules. We will also present estimates assuming "best case" (i.e., probability of event = 0) and "worst case" (i.e., probability of event = 1) scenarios, as a sensitivity analysis.

#### **6.2.2 Virologic Estimands**

Secondary Objective 3: To assess antiviral activity of CAB LA + RPV LA in adolescents living with HIV who are virologically suppressed through Week 24 and through Week 48 (Cohort 2A: oral followed by injectable)/through Week 20 and through Week 44 (Cohort 2B: injectable only).	
Estimand	Probability of a virologically suppressed adolescent (aged 12 to <18 years) living with HIV-1, who was either exclusively treated with the combination of RPV and CAB at the final recommended dose for 24 weeks (for oral lead-in) or 20 weeks (for direct to injection), experienced a severe, potentially life-threatening, or death event attributable to CAB and/or RPV, or permanently discontinued CAB and/or RPV due to a related toxicity, having virologic failure (plasma HIV-1 RNA $\geq$ 50 copies/mL; plasma HIV-1 RNA $\geq$ 200 copies/mL) through 24/48 weeks (for oral lead-in) or 20/44 weeks (for direct to injection).
Treatment	30 mg CAB + 25 mg RPV once daily orally for four weeks followed by IM injections of 600 mg CAB LA + 900 mg RPV LA (first and second injections four weeks apart with subsequent injections every eight weeks) or direct to IM injections of 600 mg CAB LA + 900 mg RPV LA (first and second injections four weeks apart with subsequent injections every eight weeks).
Target population	Analysis set

Virologically suppressed children and adolescents 12 to <18 years of age living with HIV-1 exclusively treated with the combination of RPV and CAB at the final recommended dose for either 24/48 weeks (for oral lead-in) or 20/44 weeks (for direct to injection).
	
Participants who are exclusively treated with the combination of RPV and CAB at the final recommended dose and either completed all treatment regimen through the Week 24/48 (Cohort 2A)/Week 40/44 (Cohort 2B) visit or experienced any of the following:
 
 
• death that is attributable to the study product(s), OR
 
• study product-related Grade 3 or higher adverse event (excluding injection-site AEs), OR
 
• permanent discontinuation from treatment due to study product-related toxicities (regardless of grade) during these weeks of treatment.
 


Variable(s)
 
Occurrence of virologic failure through 24/48 weeks (oral lead in)/through 20/44 weeks (direct to injection):
 
 
• Plasma HIV-1 RNA <math>\geq</math>50 copies/mL
 
• Plasma HIV-1 RNA <math>\geq</math>200 copies/mL
 
	
Outcome measure(s)
 
Occurrence of virologic failure through Week 24 and through Week 48 (Cohort 2A)/through Week 20 and through Week 44 (Cohort 2B):
 
 
• Plasma HIV-1 RNA <math>\geq</math>50 copies/mL, per snapshot algorithm
 
• Plasma HIV-1 RNA <math>\geq</math>200 copies/mL, per snapshot algorithm
 

Handling of intercurrent events
 
The following intercurrent events are relevant to the estimand:
 
 
1. Discontinuation of CAB and/or RPV due to toxicity
 
2. Death related to CAB and/or RPV
 
 
These intercurrent events (1, 2) will be addressed as specified in the snapshot algorithm.
 
 
3. Discontinuation of CAB and/or RPV due to non-toxicity reasons
 
	
Handling of missing data
 
Missing data will be handled as described in the snapshot algorithm.

4. Death unrelated to CAB and/or RPV  These intercurrent events (3, 4) will be addressed using a principal stratum approach.	
Population-level summary measure	Analysis approach

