## 2 Study Overview

### 2.1 Overview of Study Design

IMPAACT 2017 is a Phase I/II, multi-center, open-label, non-comparative dose-finding study with the primary objective of evaluating the safety, acceptability, tolerability, and pharmacokinetics of oral cabotegravir (CAB) and long-acting injectable cabotegravir (CAB LA) as well as long-acting injectable rilpivirine (RPV LA) in virologically suppressed children and adolescents living with HIV-1 aged 12 to < 18 years.

The study design includes two cohorts of participants (Cohort 1 and Cohort 2) and five study steps. In Cohort 1 Step 1, participants received either oral CAB or oral RPV for at least 4 weeks and up to 6 weeks (maximum). In Cohort 1 Step 2, participants received injectable formulations of the study products, either CAB LA or RPV LA. Cohort 1 participants were assigned either CAB (Cohort 1C) or RPV (Cohort 1R) based on their pre-study cART regimen, and all participants continued their pre-study cART regimen during Cohort 1.

Cohort 2 participants discontinue their pre-study cART regimen and receive both study products, CAB and RPV, at the doses established in Cohort 1. Cohort 2 participants may enroll to either Cohort 2A to receive both oral CAB + oral RPV (Step 3) followed by both CAB LA + RPV LA (Step 4) or Cohort 2B to directly receive both CAB LA + RPV LA without an oral lead-in phase (Step 5). Unless otherwise specified, the term 'Cohort 2' applies to participants in both Cohort 2A and Cohort 2B.

Cohort 2 Treatment under Protocol Version 4.0:

- Cohort 2A (oral lead-in followed by injections): 30 mg CAB + 25 mg RPV once daily orally for at least four weeks, and up to a maximum of 6 weeks, during Step 3 oral phase, followed by intramuscular (IM) injections of CAB LA + RPV LA: first and second injections four weeks apart (CAB LA 600 mg injection + RPV LA 900 mg injection), with subsequent injections every eight weeks through and including Week 96 (CAB LA 600 mg injections + RPV LA 900 mg injections) during Step 4 injection phase.
- Cohort 2B (start with injections): IM injections of CAB LA + RPV LA: first and second injections four weeks apart (CAB LA 600 mg injection + RPV LA 900 mg injection), with subsequent injections every eight weeks through and including Week 92 (CAB LA 600 mg injections + RPV LA 900 mg injections) during Step 5 injection phase.

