### **2.3.2 Secondary Objectives**

The secondary objectives for Cohort 2 (discontinuing a background cART regimen) are:

- 2.3.2.1 To assess safety of CAB LA + RPV LA in adolescents living with HIV who are virologically suppressed through:
- Week 48 (Cohort 2A: oral followed by injectable);
  - Week 44 (Cohort 2B: injectable only).
- 2.3.2.2 To evaluate repeat-dose pharmacokinetics of CAB LA + RPV LA in adolescents living with HIV who are virologically suppressed through:
- Week 24 and through Week 48 (Cohort 2A: oral followed by injectable);
  - Week 20 and through Week 44 (Cohort 2B: injectable only).
- 2.3.2.3 To assess antiviral activity of CAB LA + RPV LA in adolescents living with HIV who are virologically suppressed through:
- Week 24 and through Week 48 (Cohort 2A: oral followed by injectable);
  - Week 20 and through Week 44 (Cohort 2B: injectable only).

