## **4 Analysis Sets**

The following analysis sets are defined:

**All Treated:** All participants who took at least one dose of any study product in Cohort 2

**Evaluable:** For analysis purposes, evaluable participants will be defined as having been treated exclusively on the final recommended dose and either (1) having completed all treatment regimen through Week 24 (Cohort 2A)/Week 20 (Cohort 2B) or (2) having experienced any of the following:

- death that is attributable to the study product(s), OR
- study product-related Grade 3 or higher event (excluding injection-site AEs), OR
- permanently discontinued from treatment due to study product-related toxicities (regardless of grade) during these weeks of treatment.

Notes:

- An additional requirement for inclusion in the primary analyses for Cohort 2 is that the participants must be directly accrued to this cohort and be exclusively treated with the combination of the two study products; this will be approximately 70 participants.

- Oral bridging in Cohort 2 will not be counted as a substitute for an injection but as long as the recommended number of injections were given through Week 24/Week 20, even if they were out of window, the participant will be considered evaluable.

**Cohort 1 Rollover:** Cohort 2 participants who were previously enrolled to Cohort 1.

**Cohort 1-Naïve:** Cohort 2 participants who were enrolled directly to Cohort 2 without prior participation in Cohort 1.

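### The virologic analysis set in SAP Section 6.2.2 has the wrong first time point for Cohort 2B (Week 40, not Week 20), and the SAP gives two conflicting sets for the Week 48/44 virologic result

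*SAP*

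**What the plan says.** The virologic table in SAP Section 6.2.2 covers two time points per group and describes who is analysed in three places.

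- **Estimand, exposure clause:** treated "at the final recommended dose for 24 weeks (for oral lead-in) or 20 weeks (for direct to injection". Weeks 48 and 44 do not appear in this clause. The same sentence ends with an outcome clause that does cover both time points: "through 24/48 weeks (for oral lead-in) or 20/44 weeks (for direct to injection".
- **Target population:** treated "for either 24/48 weeks (for oral lead-in) or 20/44 weeks (for direct to injection".
- **Analysis set:** participants who "completed all treatment regimen through the Week 24/48 (Cohort 2A)/Week 40/44 (Cohort 2B) visit", or who had a related death, a related Grade 3 or higher event other than at the injection site, or permanent discontinuation for related toxicity.

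Elsewhere, the secondary objective in Section 2.3.2 sets the Cohort 2B time points at "Week 20 and through Week 44 (Cohort 2B: injectable only", and the outcome measures in 6.2.2 run "through Week 24 and through Week 48 (Cohort 2A)/through Week 20 and through Week 44 (Cohort 2B". Section 4 defines Evaluable at one time point only: "having completed all treatment regimen through Week 24 (Cohort 2A)/Week 20 (Cohort 2B", with the same alternative of a qualifying event. Section 5 then assigns the primary and secondary outcome measures alike to Cohort 1-naïve participants who are evaluable under that definition.

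**The concern.** There are two separate faults.

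The first is the Week 40 entry. It is probably a slip, but it sits in the inclusion rule that a programmer would code. Taken at face value, the Week 20 result in Cohort 2B would be limited to people who stayed on treatment for a further 20 weeks or had a qualifying event. Cohort 2A would face no such condition at Week 24. Someone viraemic in the Week 20 window and then withdrawn for lack of efficacy is exactly the kind of person this rule would remove.

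The second cannot be settled by reading past a typing error. For the Week 48/44 result, some parts of the SAP point to participants evaluable at Week 24/20 and others to completers of Week 48/44. The endpoint is a failure proportion and lack-of-efficacy withdrawals count as failures, so the choice can change the numerator as well as the denominator. If it is left open until data are seen, it could be made with the results in view.

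**Working it through.** This is a matter of consistency, so no power or sample-size formula applies.

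**Step 1. Cohort 2B virologic time points, place by place (SAP).**

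- Section 2.3.2, objective: 20 and 44
- Section 3.2, outcome measures: 20 and 44
- Section 6.2.2, objective line: 20 and 44
- Section 6.2.2, estimand outcome clause: 20/44
- Section 6.2.2, target population: 20/44
- Section 6.2.2, variables and outcome measures: 20 and 44
- Section 6.2.2, analysis set: **40/44**

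Only the last disagrees.

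**Step 2. Is Week 40 a Cohort 2B injection week?** Section 2.1 has the first two injections four weeks apart, then continues "with subsequent injections every eight weeks through and including Week 92" for Cohort 2B, and to Week 96 for Cohort 2A. Counting back from the last injection gives the nominal weeks:

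- Cohort 2B: 0, 4, 12, 20, 28, 36, 44, ..., 92
- Cohort 2A: 4, 8, 16, 24, 32, 40, 48, ..., 96

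Weeks 20 and 44 are on the Cohort 2B list. Week 40 is only on the Cohort 2A list.

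Injections needed to qualify by completion:

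- Cohort 2A through Week 24: 4; through Week 48: 7
- Cohort 2B through Week 20: 4; through Week 44: 7
- Cohort 2B through Week 40, read literally: 6

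With Week 20 the two groups match at both time points (4 and 4, 7 and 7). With Week 40 they do not match at the first (4 and 6).

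**Step 3. Who is lost at Week 20 under the literal rule?** A Cohort 2B participant who completed Week 20, stopped before Week 40, and had no qualifying related event. If that person had a viral load at or above the cut-off in the Week 20 window, the snapshot table in Attachment 2 scores a failure, but the person is no longer in the set.

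Size: the SAP gives about 70 evaluable. Two further inputs are assumptions: half in Cohort 2B (70 × 0.5 = 35), and 5 to 15% stopping between Weeks 20 and 40.

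- 35 × 0.05 = 1.75
- 35 × 0.15 = 5.25

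That is about 2 to 5 people. It is an upper range, because anyone who stops for related toxicity stays in. If one of those excluded were the only failure, the Cohort 2B result would go from 1/35 = 2.9% to 0/34 = 0%.

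**Step 4. Which set applies at Week 48/44?**

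- Pointing to Week 24/20: the exposure clause of the estimand, and Section 4 as applied by Section 5.
- Pointing to Week 48/44: the target population and analysis-set cells of 6.2.2.

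The Week 48/44 safety estimand in Section 6.2.1 does write 48 and 44 weeks in its exposure clause. This suggests that the 24/20 in the virologic table was carried over from the primary table, but does not prove it.

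**Step 5. Does the choice matter?** Take a participant who completes Week 24/20 and withdraws for lack of efficacy before the Week 48/44 window, with the last on-treatment viral load at or above the cut-off and no qualifying event. Attachment 2 lists lack of efficacy among the non-safety reasons, scores this person as a failure, and says that the same process will be used for Week 48.

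- Week 24/20 set: in the denominator and counted as a failure.
- Week 48/44 completer set: did not complete, so in neither numerator nor denominator.

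For illustration, with 70 in the Week 24/20 set and this person the only failure and the only exclusion, the result is 1/70 = 1.4% or 0/69 = 0%.

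**The case against.** The strongest reply is that Week 40 is one wrong number in one cell of a secondary table. The neighbouring cells say Week 20, and Sections 4 and 5 define and apply an Evaluable set at Week 20, so literal use is unlikely. No sample size, alpha or power figure depends on it. That is fair as to likelihood, but it does not make the inclusion rule correct, and it leaves the Week 48/44 conflict untouched.

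A reader might also infer more than the SAP supports:

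- **That the estimand uses only Week 24/20 throughout.** Only its exposure clause does; the outcome clause names both time points.
- **That everyone who fails or leaves between Weeks 20 and 40 is removed.** Those with a qualifying related event stay in, and virologic failure alone removes nobody who completes treatment.
- **That all later rebound is lost from the Week 20 result.** The snapshot uses the Week 20 window, so rebound first seen after it was never part of that result.
- **That these participants vanish from the report.** The supplementary virologic analysis takes all treated participants, so the loss is confined to the main result.
- **That the set could not be formed at the Week 24/20 data lock.** Section 1.1 times safety analyses there and gives no lock date for virology.
- **That the target population cell is right and the exposure clause wrong for Week 48/44.** The exposure clause agrees with Sections 4 and 5, so it may be the intended text.

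**Conclusion.** The point holds in two parts. The Week 40 entry is an error: it contradicts every other statement of the Cohort 2B virologic time points and falls on no Cohort 2B injection week. Its literal effect is limited to the main Week 20 result in Cohort 2B and to people who stop between Weeks 20 and 40 without a qualifying related event. The number cannot be derived from the SAP. The range of at most about 2 to 5 rests on an assumed 35 in Cohort 2B and an assumed 5 to 15% stopping, and falls if some stops are for related toxicity.

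The Week 48/44 conflict is the part that needs a decision. The SAP supports two denominators, and a lack-of-efficacy withdrawal after Week 24/20 can count as a failure in one and be left out of the other. With few failures expected to separate the results, a single such person could decide whether the main proportion is zero. The documents do not show which set was intended.

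**What to change.** 1. In the analysis-set cell of Section 6.2.2, replace Week 40/44 with Week 20/44 for Cohort 2B.
2. Before database lock, name one analysis set for the Week 24/20 virologic result and one for the Week 48/44 result. For the latter, state explicitly whether it is the participants evaluable at Week 24/20 or those who completed Week 48/44 or had a qualifying event, and give the reason.
3. Carry that choice through the Evaluable definition in Section 4, the statement in Section 5, and the estimand, target population and analysis-set cells of Section 6.2.2. If a Week 48/44 set is used, define it in Section 4, which now covers only Week 24/20.

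The cost is one SAP correction and a check of the code in the analysis implementation plan. No new data are needed and the sample size is unaffected.

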## **2.2 Hypothesis**

Cohort 2: The selected dose of CAB LA and RPV LA, when given as dual therapy to stable, virologically suppressed adolescents living with HIV will maintain viral suppression and will be safe through Week 24 (for Cohort 2A oral followed by injectable) and through Week 20 (for Cohort 2B injectable only) in adolescents.

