### **3.2 Secondary Safety and Viral Suppression Outcome Measures**

Safety through Week 48 (Cohort 2A)/through Week 44 (Cohort 2B):

- Any adverse event, regardless of grade
- Grade 3 or higher adverse event
- Grade 3 or higher adverse event assessed as related to study product(s)
- Serious adverse event meeting ICH criteria assessed as related to study product(s)
- Permanent discontinuation of study product due to adverse event assessed as related to study product(s)
- Death due to adverse events assessed as related to study product(s)

Virologic activity through Week 24 and through Week 48 (Cohort 2A)/through Week 20 and through Week 44 (Cohort 2B):

- Plasma HIV-1 RNA  $\geq 50$  copies/mL, per snapshot algorithm
- Plasma HIV-1 RNA  $\geq 200$  copies/mL, per snapshot algorithm

NOTE: PK outcome measures are described in the PK SAP.

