**8     Associated Documents**

**Attachment 1: Writing Team Roster**

**Attachment 2: Snapshot Algorithm (using cut-off of HIV-1 RNA 200 copies/mL)**

Condition (‘Week 24’ indicates Week 24 window/‘Week 20’ indicates Week 20 window)	Response	Reasons
1. If non-permitted change in background therapy prior to Week 24/Week 20	HIV1-RNA $\geq$ 200	Change in ART
2. If permitted change in background therapy prior to Week 24/Week 20 AND the latest on-treatment VL prior to/on the date of change is $\geq$ 200 copies/mL	HIV1-RNA $\geq$ 200	Change in ART
3. If non-permitted change in background therapy during Week 24/Week 20 
 
Last on-treatment VL during Week 24/Week 20 prior to/on the date of change <math>\geq</math> 200 copies/mL
 
Last on-treatment VL during Week 24/Week 20 prior to/on the date of change <200 copies/mL
 
No VL during Week 24/Week 20 prior to/on the date of change
 
	HIV1-RNA $\geq$ 200 HIV1-RNA < 200 HIV1-RNA $\geq$ 200	Data in window and HIV-1 RNA $\geq$ 200 copies/mL  Change in ART
4. If permitted change in background therapy during Week 24/Week 20 AND the last on-treatment VL prior to/on the date of change is $\geq$ 200 copies/mL 
 
This last on-treatment VL occurs prior to Week 24/Week 20
 
This last on-treatment VL occurs during Week 24/Week 20 but prior to/on the date of change
 
	HIV1-RNA $\geq$ 200 HIV1-RNA $\geq$ 200	Change in ART Data in window and HIV-1 RNA $\geq$ 200 copies/mL
5. If none of the above conditions met 
 
VL available during Week 24/Week 20                             
 
Last on-treatment VL during Week 24/Week 20 <math>\geq</math> 200 copies/mL
 
Last on-treatment VL during Week 24/Week 20 < 200 copies/mL
 
 
 
No VL during Week 24                             
 
If subjects still on study (i.e. IP has not been permanently stopped up to Week 24)
 
If subjects withdraw before/during Week 24 due to
 
 
 
	HIV1-RNA $\geq$ 200 HIV1-RNA < 200 No virologic data at Week 24 Window	Data in window and HIV-1 RNA $\geq$ 200 copies/mL  On study but missing data in window

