#### **Examples from FDA guidance (cut-off of 50 copies/mL):**

##### Data in Window

Virologic outcome should be determined by the last available measurement while the patient is on treatment and continued on trial within the time window:

HIV-RNA = 580 copies/mL at Day 336, HIV-RNA below 50 copies/mL on Day 350. This should be categorized as HIV-RNA below 50 copies/mL.

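### The virologic estimand counts failure through a period, but the snapshot scores the end of it, so a rebound that re-suppresses on unchanged treatment is not counted

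*SAP*

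**What the plan says.** SAP Section 6.2.2 gives the estimand variable as "Occurrence of virologic failure through 24/48 weeks (oral lead in)/through 20/44 weeks (direct to injection"), at cut-offs of 50 and 200 copies/mL. The Variable cell does not mention the snapshot, and the Estimand row of the same table also speaks of failure *through* the weeks. The matching outcome measure reads "Occurrence of virologic failure through Week 24 and through Week 48 (Cohort 2A)/through Week 20 and through Week 44 (Cohort 2B"), and each cut-off listed under it ends "copies/mL, per snapshot algorithm". Section 3.2 has the same pairing: "Virologic activity through Week 24 and through Week 48 (Cohort 2A)/through Week 20 and through Week 44 (Cohort 2B"), scored by snapshot.

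Attachment 2 sets out the algorithm. If none of its background-therapy conditions applies and a viral load exists in the window, rule 5 decides by the last on-treatment value there; the non-failing branch is "Last on-treatment VL during Week 24/Week 20 < 200 copies/mL". The attached guidance text states the principle: "Virologic outcome should be determined by the last available measurement while the patient is on treatment and continued on trial within the time window". Its worked example is "HIV-RNA = 580 copies/mL at Day 336, HIV-RNA below 50 copies/mL on Day 350", which it classes as below 50.

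The Section 2.2 hypothesis is also about a period: the selected doses "will maintain viral suppression and will be safe through Week 24" for Cohort 2A, with Week 20 as the counterpart for Cohort 2B.

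**The concern.** An occurrence through a period and a state at its end are different quantities. This SAP uses the first construction with a definite meaning elsewhere: in Section 6.1 and Section 6.2.1, safety events occurring through a given week are summarised as the probability of at least one event. A reader will carry that meaning into Section 6.2.2, where it does not describe what is computed.

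What is at stake is the conclusion that can be drawn about maintaining suppression. Section 1.1 says that these estimands serve the primary manuscript(s) and ClinicalTrials.gov reporting, and that the study will support regulatory submissions. With few failures expected among roughly 70 evaluable participants, one or two rebounds that re-suppress mark the difference between reporting none and reporting some. As worded, a zero from the snapshot could be read as no failure at any time through Week 24 or Week 48, which the snapshot does not establish.

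**Working it through.** **1. Stated variable against scoring rule**

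| Element | Where | What it captures |
|---|---|---|
| Estimand and Variable | SAP 6.2.2 | Failure occurring through 24/48 or 20/44 weeks; snapshot not named in the Variable cell |
| Outcome measure | SAP 3.2 and 6.2.2 | Same cumulative wording, scored by snapshot |
| Rule 5, data in window | Attachment 2 | Last on-treatment value in the window |
| Sensitivity and supplementary analyses | SAP 6.2.2 | Quantification limit, missing data and All Treated set, all within the snapshot |

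No row counts a value at or above the cut-off earlier in the period when the participant stays on unchanged treatment and is suppressed at the last in-window test. The cells for the population-level summary and analysis approach in the 6.2.2 table are not legible in the text available, so nothing here rests on them.

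**2. The SAP's own example, classified both ways**

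Values: 580 copies/mL at Day 336, below 50 at Day 350. The window in the attached guidance text is Days 294 to 377, so both values lie inside it.

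- Snapshot (last value in window): below 50, so not a failure at either cut-off.
- Occurrence through the period (any value at or above the cut-off): 580 ≥ 50 and 580 ≥ 200, so a failure at both.

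The two definitions give opposite answers. The example is an in-window retest. A rebound before the window is treated the same way by rule 5, since earlier values are not consulted once an in-window value exists, but the SAP gives no example of that case.

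**3. Interval method, checked on the plan's own figures**

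Exact (Clopper-Pearson) 95% limits for k events in N: lower = the 0.025 quantile of Beta(k, N−k+1), with 0 if k = 0; upper = the 0.975 quantile of Beta(k+1, N−k). The only precision figures in the SAP are those in Table 1 (Section 2.4), for adverse events. All four reproduce:

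| k/N | Table 1 | Recomputed |
|---|---|---|
| 0/70 | 0.00, 0.05 | 0, 0.0513 |
| 0/100 | 0.00, 0.04 | 0, 0.0362 |
| 14/70 | 0.11, 0.31 | 0.1139, 0.3127 |
| 20/100 | 0.13, 0.29 | 0.1267, 0.2918 |

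**4. Illustration of the gap**

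N = 70 is the approximate size of the primary analysis set in Section 4. Suppose no snapshot failures and k participants who rebounded and re-suppressed on unchanged treatment. The values of k are assumptions; the SAP gives no rate.

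| Assumed k | Snapshot (95% CI) | Cumulative k/70 (95% CI) |
|---|---|---|
| 1 | 0% (0 to 5.1%) | 1/70 = 1.4% (0.04 to 7.7%) |
| 3 | 0% (0 to 5.1%) | 3/70 = 4.3% (0.9 to 12.0%) |
| 5 | 0% (0 to 5.1%) | 5/70 = 7.1% (2.4 to 15.9%) |

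The snapshot column does not change with k.

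**The case against.** The best defence is that the calculation is not ambiguous. Every virologic outcome measure carries the snapshot label, Attachment 2 sets out the Week 24/Week 20 classification and says the same process will be mapped for Week 48, and no analyst would compute anything else. That stands. It makes this a mismatch between the estimand and its measure, not a gap in the specification. A reader might infer that the published figure would be false; that would follow only if the snapshot label were dropped, and the SAP attaches it.

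Three further inferences go beyond the document:

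- *That the snapshot looks at nothing but the last viral load in the window.* It also counts as failure a non-permitted background change before the window and a permitted change with a viral load at or above the cut-off. With no in-window value, it counts withdrawal for lack of efficacy or another non-safety reason when the last value was at or above the cut-off. None of these catches a rebound that re-suppresses on unchanged treatment.
- *That the cumulative proportion must always be at least the snapshot proportion.* A non-permitted change before the window is a snapshot failure whatever the viral load, so such a person may never have had a value at or above the cut-off.
- *That the snapshot is the wrong choice.* Nothing in the SAP supports that.

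It can also be said that maintaining suppression may be read as suppressed at entry and again at the window, that the objective is secondary in a non-comparative study, and that Section 1.1 sends outcome measures not covered here to a separate SAP. These are fair reasons to keep the snapshot as the main virologic measure and the added table descriptive. They do not reconcile the wording of Section 6.2.2 with its scoring rule.

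**Conclusion.** The point holds as a mismatch on a secondary endpoint. The estimand and Variable describe failure occurring through a period, while the scoring rule, for participants with in-window data and no background change, describes the state at the last in-window test. For a rebound followed by re-suppression on unchanged treatment, the error runs one way: the event is missed.

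The size is unknown. It depends on how many such participants occur and on the viral-load schedule, and the SAP gives neither. The illustration assumes N = 70, no snapshot failures, a chosen k, and the exact interval that the SAP specifies for its safety proportions. It shows only that small counts matter at this sample size. The conclusion rests on reading *through* in Section 6.2.2 as it is used in the safety estimands, and on the SAP alone; a cumulative analysis planned in another document would remove the need for the extra table, but not for the rewording.

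**What to change.** 1. In Section 3.2 and in the Estimand, Variable and Outcome measure entries of Section 6.2.2, restate the snapshot endpoints as *at* the Week 24 and Week 48 windows (Cohort 2A) and the Week 20 and Week 44 windows (Cohort 2B), and name the snapshot in the Variable cell. This alone removes the contradiction.
2. To address the hypothesis in Section 2.2, add one descriptive table giving the proportion with (i) any and (ii) two consecutive on-treatment HIV-1 RNA values at or above each cut-off, 50 and 200 copies/mL, from first dose through each time point, with exact 95% CIs. These are analysis definitions only and imply no rule for managing participants. Reporting both separates isolated values from confirmed ones.

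The table would use the viral loads scheduled under the protocol. Attachment 2 already refers to on-treatment values before the window, so the SAP expects such data to exist, but the schedule should be checked in the protocol. It would not detect viraemia between scheduled tests.

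The cost is a wording change, one extra table, and possibly a less favourable figure beside the snapshot result.
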